### **6.4. Study Intervention Compliance**

Study intervention will be administered under medical supervision by the investigator or designee at the baseline (Week 0, Visit 2) and Week 2 (Visit 3) visits. The dose of study intervention and study participant identification will be confirmed prior to dispensing study drug. The date and time of each dose administered will be recorded in the source documents and will be provided to the sponsor as requested.

Beginning Week 4 (Visit 4), the participant/caregiver will be encouraged to administer the study intervention while in the clinic or at home. Participants may choose to continue to receive study drug injections administered by trained clinic staff for any visit occurring in the clinic. Home dosing must be self-administered or given by a caregiver that has received proper injection technique training.

When participants self-administer study intervention(s) at home, compliance with study intervention will be assessed at each visit. Compliance will be assessed by direct questioning, counting returned injection supplies and documented in the source documents.

A record of the number of lebrizumab injections supplies dispensed to and administered by each participant or caregiver must be maintained and reconciled with study intervention and compliance records.

### **6.5. Dose Modification**

Dose modifications of lebrizumab are not allowed in this study

### **6.6. Continued Access to Study Intervention after the End of the Study**

Lebrizumab will be made available to eligible participants who complete Visit 9 (Week 24) via the Continued Access addendum, until lebrizumab is commercially available in the US. Please refer to KGBP Protocol Addendum 3 for additional information. Otherwise, lebrizumab will not be provided after participants exit this study.

## 6.7. Treatment of Overdose

For this study, any dose of lebrikizumab greater than 500 mg (baseline and Week 2) and 250 mg Q2W (Week 4 and beyond) will be considered an overdose.

Sponsor does not recommend specific treatment for an overdose.

In the event of an overdose, the investigator/treating physician should:

- Contact the medical monitor immediately.
- Evaluate the participant to determine, in consultation with the medical monitor, whether study intervention should be interrupted or whether the dose should be reduced.
- Closely monitor the participant for any AE/SAE and laboratory abnormalities until lebrikizumab can no longer be detected systemically (at least 18 weeks).

## 6.8. Concomitant Therapy

Any medication or vaccine, including over-the-counter or prescription medicines, vitamins, antacids, and/or herbal supplements, that the participant is receiving at the time of enrollment or receives during the study must be recorded along with

- reason for use
- dates of administration including start and end dates, and
- dosage information including dose and frequency for concomitant therapy of special interest.

The medical monitor should be contacted prior to entering the participant into the study if there are any questions regarding concomitant or prior therapy.

Participants should be instructed to consult with the investigator prior to initiating any new medication (either self-administered non-prescription drugs or prescription therapy prescribed by another physician) while participating in the study. The investigator is expected to examine the acceptability of all concomitant medications, topical preparations, and dietary supplements taken by participants in the study.

The use of any concomitant medication must relate to an AE listed on the AE case report form (CRF) or the participant's medical history, unless the medication is a supplement or used as preventive care.

### 6.8.1. Permitted Treatments and Procedures

The following therapies will **be permitted** during the study:

Permitted Concomitant Medications and Vaccines	Comments
Medications	
Medications for medical conditions other than AD, e.g., hypertension and diabetes	
Low and/or mid-potency TCS, TCIs (e.g., tacrolimus and pimecrolimus), or topical PDE-4	Permitted as needed on AD lesions and must be documented in the diary.

Permitted Concomitant Medications and Vaccines	Comments
inhibitors (e.g., crisaborole) for treatment of AD	
High-potency TCS for treatment of AD	Permitted up to 10 days
Non-medicated moisturizers	
Intranasal corticosteroids	
Inhaled corticosteroids and bronchodilators to control asthma	
Single intra-articular (bursa, tendons, and ligaments) corticosteroid injection	
Non-sedating antihistamines	
Ophthalmic drugs containing antihistamines, corticosteroids, or other immunosuppressants	
Allergen immunotherapies	If on maintenance dose.
Leukotriene inhibitors	
Systemic and topical anti-infectives	For treatment of acute infections.
Sedating systemic antihistamines including, but not limited to, alimemazine, chlorphenamine, clemastine, cyproheptadine, diphenhydramine, hydroxyzine, ketotifen, and promethazine	On an as-needed basis.
Systemic or oral sleep aid medications	On an as-needed basis.
Recreational use of cannabis and cannabinoid	Not allowed for the treatment of pruritus, pain and/or AD
Vaccines	
Non-live vaccinations	Including non-live SARS-CoV-2 vaccines, RNA vaccines, vaccines with inactive viral elements, and/or non-replicating viral vectors that are clinically indicated.

Abbreviations: AD = atopic dermatitis; PDE-4 = phosphodiesterase-4; RNA = Ribonucleic acid; SARS-CoV-2 = severe acute respiratory syndrome coronavirus 2; TCI = topical calcineurin inhibitors; TCS = topical corticosteroids.

NOTE: in the context of this table, “during the study” = from screening to post-treatment safety follow-up visit.

### 6.8.2. Prohibited Treatments and Procedures

The following therapies will be prohibited during the study:

Prohibited Concomitant Medications, Vaccinations, and Procedures	Comments
Medications or procedures	
Systemic corticosteroids (IM, PO, or IV)	NOTE: If used for treatment of AEs, it will be considered as rescue medication (see Section 6.8.5).
Any investigational drug other than the study drug	
B cell-depleting biologics, including rituximab	
Other biologic agents (other than the study interventions)	
Topical JAK inhibitor for treatment of AD	Any use will be considered as rescue medication (see Section 6.8.5)
TCS (high potency)	Use for >10 days is prohibited

Prohibited Concomitant Medications, Vaccinations, and Procedures	Comments
Medications or therapies for other medical conditions known to affect AD (e.g., immunosuppressive or immunomodulating drugs, such as systemic corticosteroids, mycophenolate mofetil, IFN- $\gamma$ , JAK inhibitors, cyclosporine, azathioprine, or methotrexate; phototherapy or PUVA; or systemic PDE-4 inhibitors)	
Systemic and topical anti-infectives	For chronic treatment during the study.
Planned or anticipated major medical procedures or surgeries	
Tanning booth or parlor	
Bleach bath	
Use of cannabis or cannabinoids for the treatment of pruritus, pain, and/or AD	
Vaccines	
Live or live attenuated vaccines, as well as BCG vaccine	

Abbreviations: AD = atopic dermatitis; AE = adverse event; BCG = Bacillus Calmette-Guerin; IFN- $\gamma$  = interferon-gamma; IM = intramuscular; IV = intravenous; JAK = Janus kinase; PDE 4 = phosphodiesterase-4; PUVA = photochemotherapy; TCS = topical corticosteroids; PO = by mouth.

NOTE: in the context of this table, “during the study” = from screening to post-treatment safety follow-up visit.

### 6.8.3. Non-Medicated Moisturizers

Participants may apply a stable dose of non-medicated topical moisturizer at least twice daily for  $\geq 7$  days prior to the baseline visit and throughout the study.

The participants may continue their current over-the-counter moisturizer regimen, if approved by the investigator.

All moisturizer use should be recorded in the CRF.

### 6.8.4. Topical Treatment for Atopic Dermatitis

The goal of this Phase 3b study is to demonstrate the safety and efficacy of lebrikizumab for moderate-to-severe AD in participants with skin of color. Regular use of non-medicated, non-prescription moisturizers should be used by all participants. During this study, topical therapies may be needed if the participant experiences intolerable clinical worsening of symptoms. If needed, investigators are encouraged to recommend therapy in a staged fashion, beginning with a topical low-potency treatment first, then topical mid-potency treatment if needed. In sensitive skin areas, i.e., face, neck, intertriginous, and genital areas, only low-potency topical treatments should be used.

If AD lesions recur or a participant experiences a flare, as needed use of low- and/or mid-potency TCS, TCI (tacrolimus or pimecrolimus), and/or topical PDE4 inhibitors (crisaborole) may be initiated at the participant’s discretion but must be communicated to the investigator and documented in the patient diary or as concomitant medications. . Escalation to high-potency topical corticosteroid medications should only occur if participants do not respond adequately after at least 7 days of low- or mid-potency TCS, TCI, and/or topical PDE4 inhibitors.(Section 6.8.5). Use of high-potency TCS for more than 10 days is considered rescue

therapy. Participants that receive Rescue Therapy must be discontinued from the study (see Section 7.1). All topical prescription therapy usage must be recorded in the CRF or diary.

#### **6.8.5. Rescue Medicine for Atopic Dermatitis**

The goal of this Phase 3b study is to demonstrate the safety and efficacy of lebrikizumab for moderate-to-severe AD in participants with skin of color. To be consistent with real world practice, defined topical medications are allowed in this study (see Section 6.8.4). Rescue therapies may be needed if the participant experiences intolerable clinical worsening of symptoms. Escalation to high-potency topical TCS, topical JAKs, phototherapy, and/or systemic medications, including but not limited to corticosteroids, immunosuppressants, biologics, small molecules, etc., for the treatment of AD should only occur if participants do not respond adequately after at least 7 days of low- or mid-potency TCS, TCI, and/or topical PDE4 inhibitors. Any use of topical JAKs, phototherapy, and/or systemic medications will be considered Rescue Therapy. Use of high-potency TCS for more than 10 days is also considered Rescue Therapy. Participants that receive Rescue Therapy must be discontinued from the study (see Section 7.1). All rescue medication must be recorded in the CRF.

## 7. Discontinuation of Study Intervention and Participant Discontinuation/Withdrawal

Discontinuation of specific sites or of the study as a whole are handled as part of Appendix 1.

### 7.1. Discontinuation of Study Intervention

When necessary, a participant may be permanently discontinued from study intervention. If so, the participant will remain in the study to complete procedures for an early discontinuation visit and post-treatment follow-up, if applicable, as shown in the SoA.

A participant should be permanently discontinued from study intervention if

- the participant becomes pregnant during the study
- in the opinion of the investigator, the participant should permanently discontinue the study intervention for safety reasons
- the participant develops a malignancy, except for successfully treated basal or squamous cell skin carcinoma
- the participant tests positive for HBV DNA (see Section 8.2.3)
- the participant tests positive for HCV RNA (Section 8.2.4)
- if the participant experiences a hepatic event or liver test abnormality as specified in the liver chemistry stopping criteria (see Section 7.1.1)
- the participant develops HIV infection
- the participant develops any infection that is opportunistic, such as active tuberculosis and other infections whose nature or course may suggest an immuno-compromised status
- the participant requires rescue medication treatment for symptoms of AD in the treatment period, and
- the participant has an AE or an SAE or a clinically significant change in a laboratory value that, in the opinion of the investigator, merits discontinuation of study intervention and appropriate measures being taken.

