### 7.1.1. Liver Chemistry Stopping Criteria

The study drug should be interrupted and close hepatic monitoring initiated (see Section 8.2.2) if 1 or more of these conditions occur:

Elevation a	Exception a
ALT or AST >8x ULN	
ALT or AST >5x ULN for more than 2 weeks	
ALT or AST >3x ULN and either TBL >2x ULN or INR >1.5	For participants with Gilbert's syndrome: If baseline direct bilirubin is >0.5 mg/dL, then doubling of direct bilirubin should be used for drug interruption decisions rather than TBL >2x ULN.
ALT or AST >3x ULN with the appearance of fatigue, nausea, vomiting, right upper quadrant pain or tenderness, fever, and/or rash	
ALP >3x ULN, when the source of increased ALP is the liver	
ALP >2.5x ULN and TBL >2x ULN	For participants with Gilbert's syndrome: If baseline direct bilirubin is >0.5 mg/dL, then doubling of direct bilirubin should be used for drug interruption decisions rather than TBL >2x ULN.
ALP >2.5x ULN with the appearance of fatigue, nausea, vomiting, right upper quadrant pain or tenderness, fever, and/or rash	
Source: FDA Guidance for Industry: Drug-Induced Liver Injury: Premarketing Clinical Evaluation, July 2009 and other consensus guidelines, with minor modifications	

Abbreviations: ALP = alkaline phosphatase; ALT = alanine aminotransferase; AST = aspartate aminotransferase; INR = international normalized ratio; TBL = total bilirubin; ULN = upper limit of normal.

a All ULN values should be age adjusted (AAULN) for participants <18 years of age.

Resumption of the study intervention can be considered only in consultation with the Lilly-designated medical monitor and only if liver test results return to baseline and if a self-limiting non-drug etiology is identified. Otherwise, study intervention should be discontinued.

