### 7.1.2. Temporary Discontinuation of Study Intervention

Temporary withholding of study intervention is required if the participant meets any of the following infection-related criteria during the study:

- Serious or opportunistic infections, as defined in Section 5.2. Study intervention is to be withheld until resolution of all acute clinical signs and symptoms, and completion of all appropriate anti-infective treatment.
- HBV DNA results that are reported as positive, or as detecting HBV DNA, but HBV DNA is below the level of quantification. In this situation, the sponsor's designated medical monitor should be contacted regarding the participant's status. HBV DNA testing is to be repeated as soon as is feasible. If HBV DNA is confirmed as positive, the participant must be permanently discontinued from study intervention as described in Section 7.1.
- If a participant <18 years of age loses a clinically significant amount of weight (below 40 kg), the investigator should assess rationale for weight loss and use clinical judgment to determine if the participant should temporarily discontinue the treatment.

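### Protocol Section 7.1 requires permanent discontinuation when a liver stopping criterion is met, while Section 7.1.1 interrupts drug on the same criteria and permits conditional resumption

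*Protocol*

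**What the plan says.** Protocol Section 7.1 introduces its list with "A participant should be permanently discontinued from study intervention if". One entry reads "if the participant experiences a hepatic event or liver test abnormality as specified in the liver chemistry stopping criteria", with a reference to Section 7.1.1. The entry carries no exception and no route back to treatment.

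Section 7.1.1 sets out the criteria in a table of seven elevations. The action it attaches to meeting one or more of them is different: "The study drug should be interrupted and close hepatic monitoring initiated". The exception for Gilbert's syndrome is worded the same way: "doubling of direct bilirubin should be used for drug interruption decisions". Below the table the section adds "Resumption of the study intervention can be considered only in consultation with the Lilly-designated medical monitor". Two further conditions apply: the liver tests must be back at baseline, and a self-limiting cause other than drug must have been found. The section closes with "Otherwise, study intervention should be discontinued".

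Section 7.1.2, on temporary discontinuation, begins "Temporary withholding of study intervention is required if the participant meets any of the following infection-related criteria during the study". Its list covers serious or opportunistic infection, low-level HBV DNA and weight loss in adolescents. It has no liver chemistry item.

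**The concern.** One trigger leads to two instructions. A site that acts on the Section 7.1 list stops drug for good and moves the participant to the early discontinuation visit and post-treatment follow-up. A site that acts on Section 7.1.1 holds drug, monitors, and may later discuss resumption with the medical monitor. Two participants with the same liver event could be managed differently, and a site that takes the permanent step first may already have moved the participant off the visit schedule before the Section 7.1.1 evaluation is finished.

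There is also a data consequence. Discontinuation of drug for a hepatic event is one of the five triggers for the hepatic safety CRF in Section 8.2.2, so that trigger can depend on the section followed. The primary estimand is restricted to participants who stay on treatment until Week 16, and the SAP's supportive estimands treat permanent discontinuation as their only intercurrent event. The choice between the two instructions can therefore change how a participant is classified in the analysis.

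**Working it through.** The plan gives no figure to reproduce on this point. The check is a comparison of text, then of timing, then of size.

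**Step 1: outcome by case**

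| Case | Section 7.1 | Section 7.1.1 | Agree? |
|---|---|---|---|
| A criterion is first met | Permanent discontinuation | Interruption and close monitoring | No |
| Tests later return to baseline, a self-limiting non-drug cause is found, and the medical monitor is consulted | Permanent discontinuation | Resumption may be considered | No |
| Any of those three conditions fails | Permanent discontinuation | Discontinuation | Yes, in the end |

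The first row applies to all seven elevations in the table. The second applies only to participants who meet all three conditions.

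**Step 2: does other text bridge the two?** Where the protocol intends an exception or a staged rule, it writes one. The malignancy entry in the Section 7.1 list has its exception inside the entry. For low-level HBV DNA, Section 7.1.2 says to withhold and retest, then refers back to Section 7.1 for permanent discontinuation if the result is confirmed, and Section 8.2.3 cites both sections. The liver entry has nothing comparable.

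**Step 3: when would a trigger be seen?** In the Schedule of Activities, clinical chemistry is drawn at screening, baseline, Week 16, Week 24, early discontinuation and Visit 801. EASI is also assessed at the Week 16 visit. The first scheduled on-treatment liver result therefore comes from the same visit as the primary endpoint. For a participant to leave the primary population before Week 16 over this conflict, the trigger would have to come from the baseline sample or an unscheduled test.

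After Week 16, Section 6.1 plans one dose for responders (Week 20) and three for inadequate responders (Weeks 18, 20 and 22). These are the main-period doses still open when a Week 16 chemistry result is acted on. The Week 24 sample falls after the last of them.

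For a participant triggered at Week 16:

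- If permanently discontinued, the participant is outside the on-treatment as-observed analysis at Week 24. If in the Treatment Period II Population, the participant's later values are set to missing and then imputed by MCMC-MI (hybrid estimand) or LOCF (hypothetical estimand), as in the SAP Section 5.2.4 table.
- If interrupted and resumed, the participant can contribute an observed Week 24 value.

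**Step 4: size per participant.** Inputs are the anticipated response rate p = 50% and n = 95 enrolled or n = 80 in the precision table (Protocol Section 9.5). Removing one responder from n lowers the observed rate by p − (np − 1)/(n − 1) = (1 − p)/(n − 1).

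- n = 95: 0.5/94 = 0.0053, or 0.53 percentage points.
- n = 80: 0.5/79 = 0.0063, or 0.63 percentage points.

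Removing one non-responder raises the rate by p/(n − 1), which is the same amount at p = 50%. The plan's own 90% interval at 50% and n = 80 runs from 40.96% to 59.04%, a half-width of (59.04 − 40.96)/2 = 9.04 points. The documents give no expected frequency of liver stopping events, so the number of participants affected cannot be derived.

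**The case against.** The best defence is that Section 7.1.1 is a subsection of 7.1 and the liver entry sends the reader there, so 7.1 names the category and 7.1.1 gives the working rule. Many sites may read it that way. But the entry refers to the abnormality specified in the criteria, not to a decision reached under 7.1.1, and its stated consequence is permanent discontinuation. The defence supplies the intended hierarchy; the text does not.

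Other parts of the defence stand and limit the point:

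- A reader might infer that Section 7.1.1 merely interrupts and then freely allows re-dosing. It does not. Resumption has three conditions, one of which is consultation with the sponsor-designated medical monitor, a check common to all sites. Discontinuation is the default.
- A reader might infer a material threat to the primary endpoint. Steps 3 and 4 of the check do not support that.
- A reader might infer that the lack of a liver item in Section 7.1.2 is a separate gap. That section is introduced as infection-related and liver interruption has its own section. Its silence shows only that it does not resolve the conflict.
- A reader might infer that the estimand leaves an interrupted and resumed participant undefined. It largely does not. The primary estimand names permanent discontinuation, alongside rescue, as what staying on treatment rules out, and SAP Sections 5.2.2 and 5.2.4 list only permanent discontinuation as an intercurrent event.

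**Conclusion.** The two sections are wrong as written. The immediate instruction conflicts for every participant who meets a liver criterion, and the final outcome conflicts for those who meet all the resumption conditions. Outside that subset both sections end in discontinuation.

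The point matters mainly for consistent conduct of a liver safety rule across sites. The effect on Week 16 EASI-75 is expected to be small: it would need a baseline-sample or unscheduled trigger, and each affected participant shifts the estimate by about 0.5 to 0.6 points against a half-width of about 9. Handling after Week 16, and the Week 24 secondary endpoints, could be affected more directly.

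This rests on the chemistry schedule being followed, on the assumed 50% response rate for the size calculation, and on few participants being affected, which the documents neither confirm nor rule out. It takes no position on which clinical rule is right.

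**What to change.** Reconcile Protocol Sections 7.1 and 7.1.1 so that both state the same action when a criterion is met and the same end point for that participant, and cross-refer each to the other. The sponsor decides which clinical rule applies.

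Whichever rule is chosen, all the affected wording has to change together. For example, deleting only the resumption paragraph from 7.1.1 would not be enough. The interruption instruction and the Gilbert's wording would remain, the interruption would have no end point, and the section's only discontinuation default would be gone.

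The cost is a sentence or so in each section and a cross-reference at the next amendment, with a memo to sites. No new procedures, data or analyses are needed.

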  25. Have had any of the following types of infection within 3 months of screening or develop any of these infections during screening:
    - a. Serious (requiring hospitalization, and/or intravenous or equivalent oral antibiotic treatment)
    - b. Opportunistic (as defined in Winthrop et al. 2015, see Section 10.9, Appendix 9)  
NOTE: Herpes zoster is considered active and ongoing until all vesicles are dry and crusted over.
    - c. Chronic (duration of symptoms, signs, and/or treatment of 6 weeks or longer)
    - d. Recurring (including, but not limited to recurring cellulitis, chronic osteomyelitis)  
NOTE: Participants with only recurrent, mild, and uncomplicated orolabial and/or genital herpes may be discussed with the sponsor's medical monitor to determine whether the participants meet this exclusion criterion.
  26. Have an active or acute infection requiring treatment with systemic antibiotics, antivirals, antiparasitics, antiprotozoals, or antifungals within 2 weeks before the baseline visit (baseline; Visit 2), or superficial skin infections within 1 week before the baseline visit.  
NOTE:  
Participants may be rescreened after infections resolves.  
Participants who have an upper respiratory infection, a vaginal candida infection, or an oral candida infection and who are being treated only symptomatically and not requiring systemic anti-infectives may be considered for enrollment if other study eligibility criteria are met. Enrollment of participants with other uncomplicated local infections should be discussed with the sponsor's designated medical monitor.

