### **8.3.3. Adverse Events of Special Interest**

The following TEAEs will be designated AE of special interest (AESI):

- conjunctivitis
- herpes infection or zoster, and
- parasitic infection or an infection related to an intracellular pathogen.

If these AESIs are reported, sites will be prompted to collect additional data. Participant records must include any follow-up information regarding these AESI. Study intervention should be discontinued if an AE is deemed persistent and if continuation of study intervention would not be in the best interest of the participant. Discuss discontinuation of study intervention with the sponsor or designee prior to implementation.

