### Examples of infections that may be considered opportunistic in the setting of biologic therapy

Bacterial	
	Bartonellosis (disseminated disease only)
	Campylobacteriosis (invasive disease only)
	Legionellosis
	Listeriosis (invasive disease only)
	Nocardiosis
	Tuberculosis
	Non-tuberculous mycobacterial disease
	Salmonellosis (invasive disease only)
	Shigellosis (invasive disease only)
	Vibriosis (invasive disease due to Vibrio vulnificus )
Viral	
	BK virus disease including polyomavirus-associated nephropathy
	Cytomegalovirus disease
	Hepatitis B virus reactivation
	Hepatitis C virus progression
	Herpes simplex (invasive disease only)
	Herpes zoster (any form)
	Post-transplant lymphoproliferative disorder (Epstein-Barr virus)
	Progressive multifocal leukoencephalopathy (PML), John Cunningham (JC) virus
Fungal	
	Aspergillosis (invasive disease only)
	Blastomycosis
	Candidiasis (invasive disease or oropharyngeal, esophageal. Not isolated lingual)
	Coccidioidomycosis
	Cryptococcosis
	Histoplasmosis
	Paracoccidioides infections
	Penicilliosis
	Pneumocystosis
	Sporotrichosis
	Other invasive molds: Mucormycosis (zygomycosis) ( Rhizopus , Mucor , and Lichtheimia ), Scedosporium/Pseudallescheria boydii , Fusarium
Parasitic	
	Leishmaniasis (visceral only)
	Strongyloidiasis (hyperinfection syndrome or disseminated disease)
	Microsporidiosis
	Toxoplasmosis
	Trypanosoma cruzi infection (Chagas' disease progression) (disseminated disease only)
	Cryptosporidiosis (chronic disease only)

Source: Based on Winthrop et al. (2015).

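### For an opportunistic infection, Protocol Section 7.1 calls for permanent discontinuation while Section 7.1.2 calls for withholding until it resolves, and nothing says which governs

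*Protocol*

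**What the plan says.** Protocol Section 7.1 (Discontinuation of Study Intervention) gives a list of events for which a participant should be permanently discontinued from study drug. One entry reads: "the participant develops any infection that is opportunistic, such as active tuberculosis and other infections whose nature or course may suggest an immuno-compromised status".

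Protocol Section 7.1.2 (Temporary Discontinuation of Study Intervention) makes temporary withholding mandatory for a list of infection-related criteria. The first is: "Serious or opportunistic infections, as defined in Section 5.2. Study intervention is to be withheld until resolution of all acute clinical signs" and symptoms, and until all appropriate anti-infective treatment is finished.

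Section 5.2, criterion 25b, handles the definition by reference ("see Section 10.9, Appendix 9"). Appendix 9 is a non-exhaustive table of examples. Its bacterial entries include "Tuberculosis" and its viral entries include herpes zoster in any form.

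For two other kinds of event the protocol does connect interruption to a final decision:

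- Section 7.1.2, for HBV DNA that is detected but below the level of quantification: hold and retest, then "If HBV DNA is confirmed as positive, the participant must be permanently discontinued from study intervention as described in Section 7.1".
- Section 7.1.1, for liver tests: "Resumption of the study intervention can be considered only in consultation with the Lilly-designated medical monitor", and only if further conditions are met; otherwise the drug is discontinued.

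Section 8.3.3 covers adverse events of special interest, which include herpes infection or zoster. It says: "Study intervention should be discontinued if an AE is deemed persistent" and continuing would not serve the participant's interest, and it asks for discussion with the sponsor first.

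**The concern.** Both sections stop dosing when the infection appears. They part on what happens once it has cleared. Under Section 7.1 the participant does not return to study drug. Section 7.1.2 sits under a heading about temporary discontinuation and gives the hold an end point, which has no purpose if the drug has already been stopped for good.

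An investigator facing an opportunistic infection can follow either section and be compliant with it. The first stake is participant safety and consistent conduct across sites.

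The second stake is smaller and concerns the analysis. The primary estimand is restricted to participants who stay on study treatment to Week 16 and is analysed as observed. For an infection before Week 16, the section that a site follows can decide whether that participant is in the primary population. It also determines what enters the SAP's summary of infection adverse events that led to permanent discontinuation (SAP Section 5.13.6.3).

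**Working it through.** The plan attaches no figure to this point, so the main check is textual.

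1. **Do the two rules cover the same events?** Section 7.1 names active tuberculosis as its own example. Section 7.1.2 takes its definition from Section 5.2, which leads to Appendix 9, where tuberculosis is listed. Appendix 9 does not divide its entries into a permanent-stop group and a hold group. Tuberculosis therefore meets both rules. Herpes zoster meets Section 7.1.2 through Appendix 9; it meets Section 7.1 as well if Appendix 9 also defines the term there, which is not stated.
2. **Does the wording set precedence?** Section 7.1 says permanent discontinuation should happen; Section 7.1.2 says withholding is required. Neither refers to the other for this event.
3. **Is there a written sequence?** There is one for low-level HBV DNA and one for liver tests. There is none for opportunistic infection, although it stands in the same list as HBV DNA.
4. **Is there a tie-breaker elsewhere?** Section 8 tells sites to discuss immediate safety concerns with the sponsor. Section 8.3.3 gives a judgement-based criterion for adverse events of special interest. Section 8.3.3.1 says the sponsor will identify which infections are opportunistic. None of them says whether Section 7.1 or 7.1.2 applies.

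**Possible effect on the primary rate.** Inputs:

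- Response rate of 50%: planning value, Protocol Section 9.5 and SAP Section 4.2.
- n = 80 (SAP Section 4.2; minimum in Protocol Section 9.5) and n = 95 (current enrolment target in the protocol), used as the numbers evaluable at Week 16. This is an assumption, since both are enrolment figures.
- Number of events before Week 16: not given. Assumed range 0 to 3.
- A participant who is held and then restarted is counted as having stayed on treatment. This too is an assumption.

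Precision, reproducing the plan first: at an observed 50% the 90% Wilson half-width is z / (2√(n + z²)), with z = 1.645 and z² = 2.706.

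- n = 80: 1.645 / (2 × √82.706) = 9.04 points, which matches the plan's table (40.96% to 59.04%).
- n = 95: 1.645 / (2 × √97.706) = 8.32 points.

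Shift from excluding k participants who share the same response status: 0.5k / (n − k).

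| n | k = 1 | k = 3 | 90% half-width |
|---|---|---|---|
| 80 | 0.5/79 = 0.63 points | 1.5/77 = 1.95 points | 9.04 points |
| 95 | 0.5/94 = 0.53 points | 1.5/92 = 1.63 points | 8.32 points |

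In counts for n = 80: 40/80 = 50.0% becomes 39/79 = 49.37% if one responder is excluded, or 40/79 = 50.63% if one non-responder is. With three of the same status it becomes 37/77 = 48.05% or 40/77 = 51.95%. If the three are mixed, the shift is smaller.

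**The case against.** The strongest reply is that the sections can be satisfied together. Section 7.1.2 sets a minimum hold and never states that dosing restarts, so a site that withholds and then stops permanently breaches neither. Section 7.1 also opens in permissive terms, and its phrase about an immunocompromised status could mark a narrower class for permanent stopping inside a wider class for withholding.

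Sponsor involvement should also limit divergence between sites. Section 8 routes immediate safety concerns to the sponsor, Section 8.3.3 requires discussion before discontinuation for the events it covers, and Section 2.3 provides for periodic trial-level safety reviews.

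Part of this stands. Resumption is implied, not written. The overlap is certain for tuberculosis and less certain for herpes zoster. Sponsor contact lowers the chance of divergent handling. The HBV DNA comparison applies only to results below the level of quantification. Section 8.3.3 is a discretionary criterion and not a third conflicting rule.

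None of it reconciles the two sections. The hold-then-stop sequence is not written for this event, although the protocol writes such sequences elsewhere. The narrower-class reading is not stated either, and it fails for tuberculosis, which Section 7.1 itself names. The contacts with the sponsor do not say which section the sponsor should apply.

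**Conclusion.** The concern holds. For at least one named infection the protocol gives two instructions that differ on whether dosing may resume, with no rule of precedence. It deserves correction on safety-conduct grounds, whatever the number of events.

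The statistical consequence is minor. With 0 to 3 events before Week 16, a 50% response rate and 80 to 95 evaluable participants, the primary rate would move by between 0 and 1.95 points, well inside the 90% half-width. The low end is more likely, because Protocol Section 2.3 reports no opportunistic infections in the earlier Phase 3 trials; the documents give no expected rate for this study. The SAP's supportive Week 16 estimands use the ITT population and keep such participants in the analysis.

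**What to change.** In the next amendment, reconcile Sections 7.1 and 7.1.2 for opportunistic infections and state which governs. If both are meant to apply, write the sequence from withholding to the final decision, as is already done for low-level HBV DNA and liver tests. Which action is right is for the sponsor's clinical team.

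Two secondary clarifications belong in the same edit: whether Appendix 9 defines the term for Section 7.1 as well as for Section 7.1.2, and how the discretionary criterion in Section 8.3.3 relates to both.

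Send sites a clarification letter. The cost is a few sentences of protocol text and the letter; no analysis needs to change.
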